## **Data Quality Portal**

The Data Quality Portal (DQP) provides a central location for site staff to manage unanswered queries and form delinquencies, monitor data quality and timeliness, generate reports, and review metrics.

The DQP is located on the CTSU members' website under Data Management. The Rave Home section displays a table providing summary counts of Total Delinquencies and Total Queries. DQP Queries, DQP Delinquent Forms, DQP Form Status and the DQP Reports modules are available to access details and reports of unanswered queries, delinquent forms, forms with current status and timeliness reports. Review the DQP modules on a regular basis to manage specified queries and delinquent forms.

The DQP is accessible by site staff that are rostered to a site and have access to the CTSU website. Staff that have Rave study access can access the Rave study data using a direct link on the DQP.

To learn more about DQP use and access, click on the Help icon displayed on the Rave Home, DQP Queries, and DQP Delinquent Forms, DQP Form Status, and DQP Reports modules.

Note: Some Rave protocols may not have delinquent form details or reports specified on the DQP. A protocol must have the Calendar functionality implemented in Rave by the Lead Protocol Organization (LPO) for delinquent form details and reports to be available on the DQP. Site staff should contact the LPO Data Manager for their protocol regarding questions about Rave Calendaring functionality.

## **Central Monitoring**

Central Monitoring (CM) Review is required for this protocol. CM allows Lead Protocol Organizations (LPOs) to remotely compare data entered in Rave to source documentation to ensure that sites are adhering to the protocol and central monitoring plan as well as accurately transcribing data from patients' charts (i.e., source data verification).

Sites can upload source documents required for CM Review as documented in the central monitoring plan using the Source Document Portal (SDP). This application is available on the CTSU members' website under Auditing & Monitoring and may also be accessed using a direct link within Rave on the CM Alert form. Site staff with the CRA or Investigator roles in Rave can view and upload source documents. Prior to saving source documents on the SDP, each site is responsible for removing or redacting any Personally Identifiable Information (PII) (note that functionality to do this redaction exists within the SDP itself). Designated LPO staff will review each document after it has been loaded on the SDP to ensure the appropriate documents have been uploaded and to ensure PII is redacted.

Additional information on the SDP is available on the CTSU members' website under Auditing & Monitoring > Source Document Portal in the Help Topics button or by contacting the CTSU Help Desk ([name] or [[contact]](mailto:[contact])).

THIS PROTOCOL IS FOR RESEARCH PURPOSES ONLY, SEE PAGE 1 FOR USAGE POLICY

## APPENDIX II: PROTOCOL CENTRAL MONITORING

Central monitoring will be required for all patients enrolled at each site. All documents must be uploaded with 2 weeks of the corresponding time point or cycle.

Monitored Data	Protocol Section	CRF Question/ Data Element	Monitoring Conditionality	Source document	CTSU Document Type	Time point
Eligibility						
Confirmation of eligible diagnosis	4.1.3	Does patient have the required diagnosis to be eligible for this study?	Required	E.g., clinical note, laboratory test report, pathology report, etc.	Clinical Note, Laboratory Report or Pathology report	Enrollment
Performance Level	4.1.6	ECOG performance status	Required	E.g., clinical note, eligibility checklist	Clinical Note, Eligibility Determination Checklist	
Adequate Bone Marrow function	4.1.8.1	Does patient have adequate bone marrow function?	Required	Laboratory test report	Laboratory Report	
Adequate Renal Function	4.1.8.2	Does patient have adequate renal function?	Required	Laboratory test report	Laboratory Report	
Adequate Cardiac Function	4.1.8.4	Does patient have adequate cardiac function?	Required	E.g., Echocardiogram, Scan Report	Clinical Note, Echocardiogram Report, or Scan Report(s)	
Date of Informed Consent	3.5	Date of Informed Consent	Required	Signed and Dated Informed Consent Document with redacted signatures	Informed Consent	
Drug Administration Elements						
Total Uproleselan (GMI-1271) dose	5.1	Total Dose:	Required	Medication administration record	Treatment Administration Document	Cycle 1 Cycle 2
Disease Evaluation Elements						
Bone Marrow Aspirate or Biopsy	8.1	Was the patient's disease status evaluated during this reporting period?	Required	E.g., Bone Marrow Biopsy and Aspirate Report, Radiology Report	Bone Marrow Biopsy and Aspirate Report, Radiology Report	Cycle 1 Cycle 2
Adverse Event Capture						
Labs/reports documenting protocol specific CTEP-AERS reportable events	13.0	Has an Adverse Event Expedited report been filed?	Conditional: If response is YES, CM is required	E.g., hospital admission report, laboratory reports, etc.	Relevant Document	Cycle 1 Cycle 2

THIS PROTOCOL IS FOR RESEARCH PURPOSES ONLY, SEE PAGE 1 FOR USAGE POLICY

### **Addressing Monitoring Findings**

In the event that this monitoring identifies unacceptable procedures or significant deviations from protocol procedures, then the site will need to submit a corrective action plan to [[contact]](mailto:[contact]) within two weeks.

In the event of significant repeated major deviations from the protocol, COGQA, in consultation with the study chair, may recommend that COG leadership suspend accrual at the site.

THIS PROTOCOL IS FOR RESEARCH PURPOSES ONLY, SEE PAGE 1 FOR USAGE POLICY

### APPENDIX III: TOXICITY-SPECIFIC GRADING

#### Bilirubin

Grade 1:	> ULN- ≤ 1.5 x ULN
Grade 2:	> 1.5 x ULN - 3.0 x ULN
Grade 3:	> 3.0 x ULN -10.0 x ULN
Grade 4:	> 10.0 x ULN

ALT: Use institutional ULN for ALT and CTCAE v 5 criteria for grading.

AST: For the purpose of this study, the ULN for AST is 50 U/L regardless of baseline.

Grade 1:	> 50 U/L - ≤ 150 U/L
Grade 2:	151 U/L -250 U/L
Grade 3:	251 U/L -1000 U/L
Grade 4:	> 1000 U/L

#### GGT:

Grade 1:	> ULN- 2.5 x ULN
Grade 2:	> 2.5 x ULN - 5.0 x ULN
Grade 3:	> 5.0 x ULN -20.0 x ULN
Grade 4:	> 20.0 x ULN

THIS PROTOCOL IS FOR RESEARCH PURPOSES ONLY, SEE PAGE 1 FOR USAGE POLICY

## APPENDIX V: BIOMARKER STUDIES

### Schedule for patients > 10kg:

Time Point	Specimen and Quantity	Send Specimens to:
Cycle 1 Day 1, Pre-dose		
	• 1-2 mL blood in sodium citrate tube for PK (required) 	Pyxant Labs
Cycle 1 Day 1, 30 minutes after start of infusion		
	• 1-2 mL blood in sodium citrate tube for PK (required) 	Pyxant Labs
Cycle 1 Day 1, 1 hour after start of infusion		
	• 1-2 mL blood in sodium citrate tube for PK (required) 	Pyxant Labs
Cycle 1 Day 1, 2 hours after start of infusion		
	• 1-2 mL blood in sodium citrate tube for PK (required) 	Pyxant Labs
Cycle 1 Day 1, 4 hours after start of infusion		
	• 1-2 mL blood in sodium citrate tube for PK (required) 	Pyxant Labs
Cycle 1 Day 6, Pre-dose		
	• 1-2 mL blood in sodium citrate tube for PK (required) 	Pyxant Labs
Cycle 1 Day 6, 30 minutes after start of infusion		
	• 1-2 mL blood in sodium citrate tube for PK (required) 	Pyxant Labs
Cycle 1 Day 6, 1 hour after start of infusion		
	• 1-2 mL blood in sodium citrate tube for PK (required) 	Pyxant Labs
Cycle 1 Day 6, 2 hours after start of infusion		
	• 1-2 mL blood in sodium citrate tube for PK (required) 	Pyxant Labs
Cycle 1 Day 6, 4 hours after start of infusion		
	• 1-2 mL blood in sodium citrate tube for PK (required) 	Pyxant Labs
End of Cycle 1		
	• 2-4 mL bone marrow in sodium heparin (green top) tube for MRD	Hematologics
End of Cycle 2		

THIS PROTOCOL IS FOR RESEARCH PURPOSES ONLY, SEE PAGE 1 FOR USAGE POLICY

	
 
2-4 mL bone marrow in sodium heparin (green top) tube for MRD
 
	Hematologics
--	---	--------------

Time from start of first infusion of uproleselan (GMI-1271) for the day. Collect 1 mL per time point for patients < 6 years old, and 2 mL per time point for patients ≥ 6 years old.

**Schedule for patients < 10kg:**

Time Point	Specimen and Quantity	Send Specimens to:
Cycle 1 Day 1, Pre-dose		
	
 
1-2 mL blood in sodium citrate tube for PK (required)
 
	Pyxant Labs
Cycle 1 Day 1, 30 minutes after start of infusion		
	
 
1-2 mL blood in sodium citrate tube for PK (required)
 
	Pyxant Labs
Cycle 1 Day 1, 1.5 hour after start of infusion		
	
 
1-2 mL blood in sodium citrate tube for PK (required)
 
	Pyxant Labs
Cycle 1 Day 1, 4 hours after start of infusion		
	
 
1-2 mL blood in sodium citrate tube for PK (required)
 
	Pyxant Labs
Cycle 1 Day 6, Pre-dose		
	
 
1-2 mL blood in sodium citrate tube for PK (required)
 
	Pyxant Labs
Cycle 1 Day 6, 30 minutes after start of infusion		
	
 
1-2 mL blood in sodium citrate tube for PK (required)
 
	Pyxant Labs
Cycle 1 Day 6, 1.5 hour after start of infusion		
	
 
1-2 mL blood in sodium citrate tube for PK (required)
 
	Pyxant Labs
Cycle 1 Day 6, 4 hours after start of infusion		
	
 
1-2 mL blood in sodium citrate tube for PK (required)
 
	Pyxant Labs
End of Cycle 1		
	
 
2-4 mL bone marrow in sodium heparin (green top) tube for MRD (required)
 
	Hematologics
End of Cycle 2		
	
 
2-4 mL bone marrow in sodium heparin (green top) tube for MRD (required)
 
	Hematologics

Time from start of first infusion of uproleselan (GMI-1271) for the day. Collect 1 mL per time point for patients < 6 years old, and 2 mL per time point for patients ≥ 6 years old.

THIS PROTOCOL IS FOR RESEARCH PURPOSES ONLY, SEE PAGE 1 FOR USAGE POLICY

## APPENDIX VI: CORRELATIVE STUDIES GUIDE

Correlative Study	Appx.	Volume per Sample (ml)	Total Volume (ml)
End of Cycle Bone Marrow for MRD	2	2-4 mL	4-8 mL
Blood for Pharmacokinetics Analysis	8-10	1-2 mL	8-20 mL
Total Blood + Bone Marrow Volume =			12-28 mL

Priority	Biomarker Name	Assay (CLIA: Y/N)	Use in the Trial (Integral, Integrated, or Exploratory) AND Purpose	Specimens Tested	Collection Time Points	Mandatory or Optional	Assay Laboratory and Lab PI c
Tissue							
1	MRD	Multi-parameter flow cytometry CLIA: Y	End of cycle disease assessment	Bone marrow or peripheral blood	End of cycles 1-2	M	[name], PhD Hematologics, Inc [name] [name]
Blood							
1	Pharmacokinetics	Multiple CLIA: N	To evaluate the C max , T max , elimination half-life, clearance and volume of distribution of GMI-1271	Plasma	See Specimen Collection Table in Section 8.3	M	GlycoMimetics, Inc [name] [name] 20850

THIS PROTOCOL IS FOR RESEARCH PURPOSES ONLY, SEE PAGE 1 FOR USAGE POLICY

## APPENDIX VII-A: PHARMACOKINETIC (PK) WORKSHEET ( $\geq 10\text{KG}$ )

COG Pt ID # \_\_\_\_\_

Please do not write patient names on this form or on samples.

Patient Weight: \_\_\_\_\_ kg

Uproleselan (GMI-1271) Dose: \_\_\_\_\_ mg/kg

Uproleselan (GMI-1271) Total Dose: \_\_\_\_\_ mg IV infusion

Blood samples will be collected in consenting patients in sodium citrate tubes at the following time points: Pre-dose, 30 minutes, 1, 2, and 4 hours after start of infusion of Cycle 1 Day 1 and Cycle 1 Day 6 for patients  $\geq 10\text{kg}$ .

Peripheral blood samples for PK analysis should be obtained as follows: For patients  $\geq 6$  years old, collect 2 mL of blood into a sodium citrate tube per timepoint. For patients  $< 6$  years old, collect 1 mL of blood into a sodium citrate tube per timepoint.

### Schedule for patients $\geq 10\text{kg}$ :

Record the exact date and time the sample is drawn.

Time Point	Scheduled Collection Time	Actual Date Sample Collected	Actual Time Sample Collected
Cycle 1, Day 1	Immediately Pre-dose	___/___/___	_  :  _
Cycle 1, Day 1	30 minutes after start of infusion ( $\pm 5$ minutes)	___/___/___	_  :  _
Cycle 1, Day 1	1 hour after start of infusion ( $\pm 20$ minutes)	___/___/___	_  :  _
Cycle 1, Day 1	2 hours after start of infusion ( $\pm 20$ minutes)	___/___/___	_  :  _
Cycle 1, Day 1	4 hours after start of infusion ( $\pm 20$ minutes)	___/___/___	_  :  _
Uproleselan (GMI-1271) Dose on Cycle 1, Day 1	Date: ___/___/___	Infusion Start Time:  _  :  _	Infusion Stop Time:  _  :  _
Time Point	Scheduled Collection Time	Actual Date Sample Collected	Actual Time Sample Collected
Cycle 1, Day 6	Immediately Pre-dose	___/___/___	_  :  _
Cycle 1, Day 6	30 minutes after start of infusion ( $\pm 5$ minutes)	___/___/___	_  :  _
Cycle 1, Day 6	1 hour after start of infusion ( $\pm 20$ minutes)	___/___/___	_  :  _
Cycle 1, Day 6	2 hours after start of infusion ( $\pm 20$ minutes)	___/___/___	_  :  _
Cycle 1, Day 6	4 hours after start of infusion ( $\pm 20$ minutes)	___/___/___	_  :  _
Uproleselan (GMI-1271) Dose on Cycle 1, Day 6	Date: ___/___/___	Infusion Start Time:  _  :  _	Infusion Stop Time:  _  :  _

One copy of this PK Form should be uploaded into RAVE. A second copy should be sent with the samples to the address listed in [Section 8.3](#), in addition to detailed guidelines for packaging and shipping PK samples.

If this form will be used as a source document, the site personnel who collected the samples must sign and date this form below:

Signature: \_\_\_\_\_  
(site personnel responsible for collection of samples)

Date: \_\_\_\_\_

THIS PROTOCOL IS FOR RESEARCH PURPOSES ONLY, SEE PAGE 1 FOR USAGE POLICY

## APPENDIX VII-B: PHARMACOKINETIC (PK) WORKSHEET (< 10 KG)

COG Pt ID # \_\_\_\_\_

Please do not write patient names on this form or on samples.

Patient Weight: \_\_\_\_\_ kg

Uproleselan (GMI-1271) Dose: \_\_\_\_\_ mg/kg

Uproleselan (GMI-1271) Total Dose: \_\_\_\_\_ mg IV infusion

Blood samples will be collected in consenting patients in sodium citrate tubes at the following time points: Pre-dose, 30 minutes, 1.5, and 4 hours after start of infusion of Cycle 1 Day 1 and Cycle 1 Day 6 for patients <10kg

Peripheral blood samples for PK analysis should be obtained as follows: For patients  $\geq 6$  years old, collect 2 mL of blood into a sodium citrate tube per timepoint. For patients < 6 years old, collect 1 mL of blood into a sodium citrate tube per timepoint.

### Schedule for patients < 10 kg:

Record the exact date and time the sample is drawn.

Time Point	Scheduled Collection Time	Actual Date Sample Collected	Actual Time Sample Collected
Cycle 1, Day 1	Immediately Pre-dose	___/___/___	_  :  _
Cycle 1, Day 1	30 minutes after start of infusion ( $\pm 5$ minutes)	___/___/___	_  :  _
Cycle 1, Day 1	1.5 hour after start of infusion ( $\pm 20$ minutes)	___/___/___	_  :  _
Cycle 1, Day 1	4 hours after start of infusion ( $\pm 20$ minutes)	___/___/___	_  :  _

Uproleselan (GMI-1271) Dose on Cycle 1, Day 1	Date: ___/___/___	Infusion Start Time:  _  :  _	Infusion Stop Time:  _  :  _
--	-------------------	----------------------------------	---------------------------------

Time Point	Scheduled Collection Time	Actual Date Sample Collected	Actual Time Sample Collected
Cycle 1, Day 6	Immediately Pre-dose	___/___/___	_  :  _
Cycle 1, Day 6	30 minutes after start of infusion ( $\pm 5$ minutes)	___/___/___	_  :  _
Cycle 1, Day 6	1.5 hour after start of infusion ( $\pm 20$ minutes)	___/___/___	_  :  _
Cycle 1, Day 6	4 hours after start of infusion ( $\pm 20$ minutes)	___/___/___	_  :  _

Uproleselan (GMI-1271) Dose on Cycle 1, Day 6	Date: ___/___/___	Infusion Start Time:  _  :  _	Infusion Stop Time:  _  :  _
--	-------------------	----------------------------------	---------------------------------

One copy of this PK Form should be uploaded into RAVE. A second copy should be sent with the samples to the address listed in [Section 8.3](#), in addition to detailed guidelines for packaging and shipping PK samples.

If this form will be used as a source document, the site personnel who collected the samples must sign and date this form below:

Signature: \_\_\_\_\_  
(site personnel responsible for collection of samples)

Date: \_\_\_\_\_

THIS PROTOCOL IS FOR RESEARCH PURPOSES ONLY, SEE PAGE 1 FOR USAGE POLICY

## **APPENDIX VIII: RESPONSE CRITERIA FOR LEUKEMIA**

### **Response Criteria:**

For patients who are enrolled onto this study with <5% blasts, complete remission will be defined only as the attainment of a MRD negative complete remission as determined by central flow cytometry. For patients enrolled onto this study with ≥5% blasts, definitions of complete, partial or incomplete count recovery will be assessed using COG-specific criteria for pediatric patients.

### **COG Response Criteria:**

#### **COG Complete Remission (COG-CR):**

Attainment of < 5% leukemic blasts in the bone marrow as determined by central flow cytometry with no evidence of circulating leukemic blasts or extramedullary disease and with recovery of peripheral blood counts (ANC ≥ 500/μL and platelet count ≥ 50,000/μL). The qualifying CBC must be drawn on the day of the marrow or up to 7 days after bone marrow. There is no requirement for bone marrow cellularity.

#### **COG CR With Partial Recovery of Platelet Count (COG-CRp):**

Attainment of < 5% leukemic blasts in the bone marrow as determined by central flow cytometry and no evidence of circulating leukemic blasts or extramedullary disease and with recovery of ANC ≥ 500/μL without platelet recovery to 50,000/μL. The qualifying CBC must be drawn on the day of the marrow or up to 7 days after bone marrow.

#### **COG CR with incomplete blood count recovery (COG-CRi):**

Attainment of < 5% leukemic blasts in the bone marrow as determined by flow cytometry and no evidence of circulating leukemic blasts or extramedullary disease and with ANC > 200/μL and platelet count > 20,000/μL without dependence on platelet transfusions (defined as: platelet count > 20,000/μL AND no platelet transfusions x 5 days). The qualifying CBC must be drawn on the day of the marrow or up to 7 days after bone marrow.

### **Aplasia:**

If a patient has a hypoplastic bone marrow for ≥ 60 days and failure to recover a peripheral ANC > 200/μL and a non-transfusion dependent platelet count > 20,000/μL not due to malignant infiltration or severe infection (defined as ≥ Grade 3).

### **MRD negative:**

Presence of < 0.05% of leukemic blasts by flow cytometry.

### **Extramedullary disease:**

The same modality (CT, MRI, and/or FDG PET) used for pre-treatment evaluation should preferably be performed for follow-up imaging. Patients will be considered in complete remission if there has been complete radiographic resolution of disease. If radiographic imaging demonstrates residual extramedullary disease, tissue biopsy should be used to determine response, if clinically feasible. If tissue biopsy is not clinically appropriate, then radiographic studies should be used to determine extramedullary disease response. The differentiation between residual disease and residual scar tissue on radiographic studies may be difficult and the final determination of radiographic disease status should be made by the treating clinician in consultation with the local radiologist.

THIS PROTOCOL IS FOR RESEARCH PURPOSES ONLY, SEE PAGE 1 FOR USAGE POLICY

### **COG Treatment Failure (COG-TF):**

Failure to achieve COG-CR, COG-CRp or COG-CRi as defined above after up to 2 cycles of therapy. Persistence of circulating leukemia blasts confirmed by flow cytometry or of extramedullary disease will also constitute treatment failure. Patients who do not have a marrow at diagnosis are not evaluable for response/TF. For patients who enroll with fewer than 5% of blasts, TF is defined as failure to achieve MRD negative COG-CR, MRD negative COG-CRp or MRD negative COG-CRi.

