### **1.2 Secondary Aims**

- 1.2.1 To describe the expression of E-selectin ligand on the surface of myeloid leukemic blasts at relapse prior to initiation of uproleselan (GMI-1271) in combination with fludarabine and cytarabine and at completion of the cycle.
- 1.2.2 To describe the antileukemic activity of uproleselan (GMI-1271) (COG-CR/CRp/CRi and rates of MRD negative response after up to two cycles of therapy) in combination with fludarabine and cytarabine within the limits of a Phase 1 study.

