### 4.1.3 Diagnosis

Patients, with or without Down syndrome (DS), and with *de novo* acute myeloid leukemia, therapy-related acute myeloid leukemia, myelodysplastic syndrome with increased blasts (MDS-IB), therapy-related myelodysplastic syndrome with increased blasts (MDS-IB) or mixed phenotype acute leukemia that expresses E-selectin ligand on the cell membrane according to APAL2020SC screening results and meet one of the following:

- Second or greater relapse or refractory AML as defined below, including isolated extramedullary disease (EMD), but excluding isolated central nervous system (CNS) or isolated testicular disease.
- Second or greater relapse or refractory myelodysplastic syndrome (MDS) with increased blasts (MDS-IB).

THIS PROTOCOL IS FOR RESEARCH PURPOSES ONLY, SEE PAGE 1 FOR USAGE POLICY

- Second or greater relapse or refractory mixed phenotype acute leukemia (MPAL).

**Note:** Documentation of E-selectin expression by multidimensional flow cytometry (MDF) at the central laboratory (Hematologics, Inc.) on the most recent bone marrow sample prior to the diagnosis of the current relapsed or refractory disease is acceptable for eligibility to this study in the event of isolated extramedullary disease, inability to obtain a bone marrow aspirate or lack of leukemic blasts in the peripheral blood.

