#### 4.1.4 Disease Status

##### 4.1.4.1 *Bone marrow relapse and MDF – MRD relapse:*

(patients must meet one of the following criteria to be defined as having relapse disease)

- A single bone marrow sample showing  $\geq 1\%$  leukemic blasts by multidimensional flow cytometry performed at the central laboratory (performed only at Hematologics through the screening study APAL2020SC).
- In cases where a bone marrow aspirate cannot be obtained because of extensive fibrosis, blast count can be obtained from touch imprints or estimated from an adequate bone marrow core biopsy; blast count must be  $\geq 5\%$  to be eligible. A complete blood count documenting the presence of at least 1,000/ $\mu\text{L}$  (i.e., a WBC count  $\geq 10,000/\mu\text{L}$  with  $\geq 10\%$  blasts or a WBC count of  $\geq 5,000/\mu\text{L}$  with  $\geq 20\%$  blasts) circulating leukemic cells (blasts) can also be used if a bone marrow aspirate or biopsy cannot be performed.

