### 8.1 Required Clinical, Laboratory and Disease Evaluation

All clinical and laboratory studies to determine eligibility must be performed within 7 days prior to enrollment unless otherwise indicated. Laboratory values used to assess eligibility (see [Section 4.0](#)) must be no older than seven (7) days at the start of therapy. Laboratory tests need not be repeated if therapy starts within seven (7) days of obtaining labs to assess eligibility. If a post-enrollment lab value is outside the limits of eligibility, or laboratory values are older than 7 days, then the following laboratory evaluations must be re-checked within 48 hours prior to initiating therapy: CBC with differential, bilirubin, ALT (SGPT), AST, and serum creatinine. If the recheck is outside the limits of eligibility, the patient may not receive protocol therapy and will be considered off protocol therapy. Imaging studies, bone marrow biopsy and/or aspirate, biopsy of extramedullary site (if the bone marrow is not involved by disease) and lumbar puncture must be obtained within 14 days prior to enrollment.

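### Appendix VIII makes patients who enter without a marrow not evaluable for response or failure, even when blood alone would show that treatment failed

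*Combined protocol and SAP*

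**What the plan says.** Entry. Section 4.1.4.1 sets a threshold of 1,000 blasts per microlitre of blood and says that "circulating leukemic cells (blasts) can also be used if a bone marrow aspirate or biopsy cannot be performed". Appendix VIII repeats this under Bone Marrow Relapse, item II. Section 4.1.4.3 points refractory disease to the same item when fibrosis prevents an aspirate. The note to Section 4.1.3 also foresees "inability to obtain a bone marrow aspirate or lack of leukemic blasts in the peripheral blood", and accepts earlier documentation of E-selectin ligand expression in that event.

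Evaluability. Two consecutive sentences in Appendix VIII, under COG Treatment Failure, deal with these patients. The first reads: "Persistence of circulating leukemia blasts confirmed by flow cytometry or of extramedullary disease will also constitute treatment failure". The second reads: "Patients who do not have a marrow at diagnosis are not evaluable for response/TF". Neither carries an exception for patients who entered on blood.

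Endpoint. Aim 1.2.2 is to describe "COG-CR/CRp/CRi and rates of MRD negative response after up to two cycles of therapy". The marrow part of COG-CR is "Attainment of < 5% leukemic blasts in the bone marrow as determined by central flow cytometry", which is a level reached after treatment and not a change from baseline. Section 11.4 treats the response analysis as descriptive and defines no response-evaluable set or denominator.

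Pre-study marrow. Section 8.1 sets a 14-day window ahead of enrollment for a group of tests that includes the marrow; its sentence begins "Imaging studies, bone marrow biopsy and/or aspirate, biopsy of extramedullary site (if the bone marrow is not involved by disease) and lumbar puncture must be". Section 4.0 has the same requirement and Table 8 lists a pre-study marrow. None of these makes an exception for the circulating-blast route.

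**The concern.** A patient who enters on blood blasts, has no marrow, and still has blood blasts after treatment falls under both sentences. The first makes that patient a treatment failure. The second says failure cannot be assessed. Nothing else in the document says which sentence prevails, and this is the only evaluability rule for response.

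If the second sentence prevails, treated patients are lost from the activity description although their outcome is known. In a trial of this size each lost patient visibly moves the percentage. Section 10.1(a) also relies on Appendix VIII for the meaning of treatment failure, so the same ambiguity reaches that criterion.

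**Working it through.** **1. Does the endpoint need a baseline marrow?**

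- COG-CR, COG-CRp and COG-CRi each combine marrow blasts below 5% after treatment, no circulating blasts or extramedullary disease, and count thresholds. None is a change from baseline.
- Failure through persistent blood blasts needs no marrow at all.
- COG-TF opens by defining failure as not reaching any of the three remission categories after up to two cycles. A patient with no qualifying post-treatment marrow already fits that definition.
- Aim 1.3.1, the relative reduction in marrow blasts, does need a baseline marrow percentage.
- A baseline blast level has one further use. Section 12.2.2 and Appendix VIII apply a stricter standard, MRD-negative remission only, to patients enrolled with fewer than 5% blasts. The document does not say how a patient known only from blood is placed.

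So the outcome can be determined without a baseline marrow once the plan says which standard applies.

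**2. The plan's own sample size.** Section 11.1 expects at most 22 patients: 6 at each of two dose levels plus 6 for PK, with 20% inevaluability.

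- 6 + 6 + 6 = 18, and 18 × 1.2 = 21.6, rounded up to 22. This matches. (18 / 0.8 = 22.5 would give 23.)
- Absolute maximum: 12 + 12 + 6 = 30, and 30 × 1.2 = 36. This matches.

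The 20% covers DLT and PK evaluability. No number is planned for response.

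**3. Effect on the reported rate.** Let N be the treated patients, x all responders, k the patients without a marrow who are excluded, and j the responders among those k. The rate in all treated patients is x/N; after exclusion it is (x − j)/(N − k). Exclusion raises the rate only when j/k is below x/N.

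The documents give neither k nor j, so k = 1 to 3 is an assumption. With N = 22 and x = 9 (close to the 41% cited in Section 2.3.1), 9/22 = 40.9%. If every excluded patient is a non-responder (j = 0):

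- k = 1: 9/21 = 42.9%, up 2.0 points
- k = 2: 9/20 = 45.0%, up 4.1 points
- k = 3: 9/19 = 47.4%, up 6.5 points

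Range over other assumed rates and sizes, with k = 3 and j = 0:

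- 6/22 = 27.3% becomes 6/19 = 31.6%
- 13/22 = 59.1% becomes 13/19 = 68.4%
- 15/36 = 41.7% becomes 15/33 = 45.5%

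If some excluded patients respond (N = 22, x = 9, k = 2):

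- j = 1: 8/20 = 40.0%
- j = 2: 7/20 = 35.0%

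Both are below 40.9%.

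**4. Against sampling error.** The exact (Clopper-Pearson) 95% interval for 9/22 is 20.7% to 63.6%; for 9/20 it is 23.1% to 68.5%. The shifts in step 3 are small beside either.

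**The case against.** The best defence is that the second sentence limits the first: persistent blasts mean failure among evaluable patients, and a patient without a baseline marrow is not evaluable. That reading removes the literal clash. It does not remove the loss, because a patient with known persistent disease is then neither a responder nor a failure.

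Several further objections stand and limit the point.

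- The rule asks for a marrow, not an aspirate. A reader might infer that all patients with fibrosis are dropped. They are not: Section 4.1.4.1 lets them enter on touch imprints or a core biopsy, and they then have a marrow.
- Sections 4.0 and 8.1 call for a pre-study marrow, so patients with none should be rare.
- A reader might infer that the response rate is inflated by dropping failures with a high disease burden. The documents give no response rate for these patients, and the rule removes responders as well. Upward bias is plausible but not shown.
- A reader might set the shift against the 41% and 25% in Section 2.3.1. Those are adult figures on a different chemotherapy backbone, and no comparison with them is planned.
- A reader might infer that only aim 1.3.1 uses a baseline marrow. The split at 5% entry blasts shows otherwise.
- A reader might infer that removal from therapy is left wholly undecided. Sections 5.2 and 10.1 contain other criteria; what is unclear is how 10.1(a) applies.
- Removal from a denominator is itself inferred from the evaluability wording, since no denominator is written. It is the natural reading.

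**Conclusion.** The point holds as an inconsistency in the response definition. Section 4.1.4.1 admits patients without a marrow. Appendix VIII then withdraws them from both response and failure, next to a sentence that would classify some of them as failures. Treated patients with a determinable outcome are lost from aim 1.2.2.

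The size is unknown and probably small. Under the assumption of 1 to 3 excluded non-responders among 22 patients with 9 responders, the rate rises by 2.0 to 6.5 points, well inside the sampling uncertainty. The shift is zero if no such patient enrols, and zero in expectation if they respond like the others. The endpoint is secondary and descriptive, and no dose decision rests on it.

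One reading is assumed. The rule's reference to diagnosis is taken to mean study entry, which fits the way Section 4.3 ties CNS status to the diagnosis of relapsed or refractory disease. The document does not define the term here.

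**What to change.** In Appendix VIII, reconcile the two COG-TF sentences and state the rule for the response analysis:

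- **Denominator:** all treated patients whose disease was documented by any route in Section 4.1.4.
- **Blood-only entrants:** failures if circulating blasts or extramedullary disease persist, or if no post-treatment marrow shows a response; responders if a post-treatment central marrow and the counts meet the criteria.
- **Response standard:** blood-only entrants are assessed under the criteria for 5% or more blasts at entry, unless the sponsor specifies otherwise.
- **Timing:** define the term for diagnosis in this rule as study entry.
- **Sensitivity line:** report the rate in patients with a baseline marrow, with the number left out.
- **Aim 1.3.1:** keep the baseline-marrow restriction.

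The pre-study marrow requirement in Sections 4.0 and 8.1 must be reconciled with the entry route in Section 4.1.4.1. The effect of the revised definition on Section 10.1(a) must also be reconciled; which removal rule applies is for the sponsor to settle.

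The cost is wording. No procedures are added. The reported response rate may come out slightly less favourable.
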